11.3.2 Sweat Chloride

The SwCl test is a standard diagnostic tool for CF, serving as a biomarker of CFTR activity. Sweat samples will be sent to a central laboratory for testing and interpretation of results. Individual SwCl test results will not be disclosed to the study sites. Specific instructions for collection, handling, processing, and shipping of SwCl samples to the central laboratory will be provided separately. The SwCl test must be conducted predose relative to the morning dose of study drug during the Treatment Periods. At each time point, 2 samples will be collected, 1 sample from each arm (left and right).

See Section 10.7 for information about access to SwCl results.

11.3.3 Multiple Breath Washout

The N₂-MBW testing will be performed in multiple replicates for each visit and the final LCI value will be calculated from the technically acceptable washout replicates by a central reader. The final LCI value at each visit will be the value provided by the LCI vendor based on the replicates.

At all visits, MBW tests should be performed “pre-bronchodilator” as described in Section 11.3.1. The MBW test should be performed before the spirometry assessment. See Section 10.7 for information about access to LCI results.

Detailed MBW procedures will be supplied separately in a Study Reference Manual.

11.3.4 Height and Weight

Height and weight will be measured with shoes off and before the dose of the study drug at each clinic visit during the Treatment Periods.

11.3.5 Cystic Fibrosis Questionnaire-Revised

The questionnaires provide information about demographics; general quality of life, school, work, or daily activities; and symptom difficulties (pertaining to CF).

Subjects/caregivers will be asked to complete the CFQ-R in their native language, if validated translations are available.^{17, 18} If there is no validated translation available in the subject’s native language, the subject will not complete the questionnaire. Copies of the CFQ-R used will be provided in the Study Reference Manual. Validated translations of the CFQ-R, if available, will be provided for participating centers with non-English-speaking populations.^{19, 20}

The CFQ-R will be completed before any other assessments are performed at that visit.

11.3.6 Other Events Related to Outcome

11.3.6.1 Antibiotic Therapy for Sinopulmonary Sign/Symptoms

New or changed antibiotic therapy (intravenous [IV], inhaled, or oral) for the following sinopulmonary signs/symptoms will be determined and documented at visits as indicated in [Table 3-1](#) and [Table 3-2](#):

- Change in sputum
- New or increased hemoptysis
- Increased cough
- Increased dyspnea
- Malaise, fatigue, or lethargy
- Temperature above 38°C (equivalent to approximately 100.4°F)
- Anorexia or weight loss
- Sinus pain or tenderness
- Change in sinus discharge
- Change in physical examination (PE) of the chest
- Decrease in pulmonary function by 10%
- Radiographic changes indicative of pulmonary infection

For this study, PEx is defined as a new or change in antibiotic therapy (IV, inhaled, or oral) for any 4 or more of the above signs/symptoms. This definition is based on the definition of a PEx used in previous clinical studies, including IVA clinical studies.^{[21, 22](#)}

It is recommended that the study drug not be interrupted during a PEx unless, in the opinion of the investigator, it would be in the best interest of the subject.

11.3.6.2 Hospitalization for CF

Subjects will be queried about planned and unplanned hospitalizations lasting ≥ 24 hours that occurred during the study. The dates of hospitalizations and the reasons for hospitalizations will be documented.

For any hospitalization (planned and unplanned), the procedures for safety reporting should also be followed.

11.4 Other Assessments

These data will be used for internal exploratory purposes and may or may not be included in the clinical study report (CSR). Detailed procedures for the collection of blood samples will be provided in a separate document.

11.4.1 FE-1 and IRT

Assessments of FE-1 and IRT will be conducted to assess exocrine pancreatic function.

Fecal samples for assessment of FE-1 will be collected at the study center during the study visit; alternatively samples may be collected by the subject's caregiver up to 24 hours before the study visit (e.g., at home) and brought to the study visit. The sample may be collected pre- or postdose.

See Section 10.7 for information about access to FE-1 and IRT results.

11.4.2 Blood Biomarkers

Blood samples for blood biomarker analysis will be collected and banked for potential exploratory evaluation of correlations between blood biomarkers (e.g., proteins, peptides, lipids, vitamins, endogenous metabolites, and RNA) with PD, treatment benefit, and AEs.

Specific instructions for the collection, processing, storage, and shipment of blood biomarker samples will be provided in the Laboratory Manual.

11.5 Safety

Safety evaluations will include reporting of AEs, clinical laboratory assessments, PEs, clinical evaluation of vital signs, pulse oximetry, standard 12-lead ECGs, and ophthalmologic examinations.

11.5.1 Adverse Events

All AEs will be assessed, documented, and reported in accordance with ICH GCP Guidelines. Section 13.1 outlines the definitions, collection periods, criteria, and procedures for documenting, grading, and reporting AEs. Electronic AE case report form (CRF) completion guidelines for investigators as well as training will be provided.

11.5.2 Clinical Laboratory Assessments

Blood and urine samples will be analyzed at a central laboratory with the exception of urine pregnancy tests, which will be analyzed locally. All blood samples will be collected while subjects are in a seated or supine position. Specific instructions for the collection, processing, and shipment of samples will be provided in a separate Laboratory Manual. Laboratory test results that are abnormal and considered clinically significant must be reported as AEs (see Section 13.1).

The safety laboratory test panels are shown in Table 11-1.

Table 11-1 Safety Laboratory Test Panels

Serum Chemistry	Hematology	Urinalysis ^a
Glucose	Hemoglobin	Leukocyte esterase
Blood urea nitrogen ^b	Erythrocytes	Nitrite
Creatinine	Mean corpuscular volume	Urobilinogen
Sodium	Platelets	Urine protein
Potassium	Reticulocytes	pH
Calcium	Leukocytes	Urine blood
Chloride	Differential (absolute and percent):	Specific gravity
Magnesium	Eosinophils	Urine ketones
Bicarbonate	Basophils	Urine bilirubin
Inorganic phosphate	Neutrophils	Urine glucose
Total and direct bilirubin	Lymphocytes	
Alkaline phosphatase	Monocytes	
Aspartate transaminase		
Alanine transaminase		
Amylase	Coagulation	
Lipase	Activated partial thromboplastin time	
Gamma-glutamyl transferase	Prothrombin time	
Protein	Prothrombin time International	
Albumin	Normalized Ratio	
Creatine kinase		
Total cholesterol		
Lactate dehydrogenase		

Note: Haptoglobin may be analyzed if judged to be clinically appropriate by the investigator.

^a If urinalysis results are positive for leukocyte esterase, nitrite, protein, or blood, microscopic examination of urine will be performed, and results will be provided for leukocytes, erythrocytes, crystals, bacteria, and casts.

^b If blood urea nitrogen cannot be collected, urea may be substituted.

Pregnancy (β -human chorionic gonadotropin) Tests for all Female Subjects: All female subjects must have a pregnancy test every 4 weeks. Serum pregnancy tests will be performed at the study site and analyzed at the central laboratory. Urine pregnancy tests will be performed and analyzed at the site or, at assessment time points when telephone contact takes the place of a clinic visit, at home by using a home kit provided by the study site. Results of a home urine pregnancy test will be reported to the site by telephone. Additional pregnancy tests may be required according to local regulations and/or requirements.

Additional Evaluations: Additional clinical laboratory evaluations will be performed at other times if judged by the investigator to be clinically appropriate.

For the purposes of study conduct and unless noted otherwise, only laboratory tests done in the central laboratory may be used. Local laboratories may be used at the discretion of the local investigator for management of urgent medical issues. If a local laboratory test value is found to be abnormal and clinically significant, it will be verified by the central laboratory as soon as possible after the investigator becomes aware of the abnormal result. If it is not possible to send a timely specimen to the central laboratory (e.g., the subject was hospitalized elsewhere), the investigator may base the assessment of an AE on the local laboratory value.

11.5.3 Physical Examinations and Vital Signs

A PE of all body systems and vital signs assessment will be performed at select study visits. At other visits, symptom-directed PEs and symptom-directed vital signs assessments can be performed at the discretion of the investigator or healthcare provider.

A PE includes a review of the following systems: head, neck, and thyroid; eyes, ears, nose, and throat; respiratory; cardiovascular; lymph nodes; abdomen; skin; musculoskeletal; and neurological. Breast, anorectal, and genital examinations will be performed when medically indicated. Any clinically significant abnormal findings in PEs will be reported as AEs.

Weight, height, and BMI (derived) will also be assessed (Section 11.3.4).

Vital signs include blood pressure (systolic and diastolic), temperature, pulse rate, and respiration rate. These will be assessed following at least a 5-minute rest in the seated or supine position.

Arterial oxygen saturation by pulse oximetry will be assessed following at least a 5-minute rest and before study drug dosing. At visits when study drug is taken at the site, pulse oximetry will be collected before study drug dosing.

11.5.4 Electrocardiograms

Standard 12-lead ECGs will be performed using a machine with printout. Additional standard 12-lead ECGs will be performed at any other time if clinically indicated. The performance of all ECGs will adhere to the following guidelines:

- The ECG will be done before any other procedures that may affect heart rate, such as blood draws.
- The subject will be instructed to rest for at least 5 minutes before having an ECG.

A printout of the ECG traces will be made for safety review by the investigator and maintained with source documentation. Clinically significant ECG abnormalities occurring during the study through completion of study participation will be recorded as AEs.

To ensure safety of the subjects, a qualified individual at the study site will make comparisons to baseline measurements. If the QTcF is increased by >60 msec from the baseline or an absolute QTcF value is ≥ 500 msec for any scheduled ECG, 2 additional ECGs will be performed approximately 2 to 4 minutes apart to confirm the original measurement. If either of the QTcF values from these repeated ECGs remains above the threshold value (>60 msec from baseline or ≥ 500 msec), a single ECG will be repeated at least hourly until QTcF values from 2 successive ECGs fall below the threshold value that triggered the repeat measurement. A subject with a QTcF value above the threshold value will discontinue dosing.

11.5.5 Ophthalmologic Examination

Ophthalmologic examinations do not need to be completed if there is documentation of bilateral lens removal for the subject.

All examinations will be conducted by a licensed ophthalmologist or optometrist and will include:

- measurement of best-corrected distance visual acuity of each eye; and
- pharmacologically dilated examination of the lens with a slit lamp.

Ophthalmologic examinations are required at select study visits in the Treatment Periods ([Table 3-1](#) and [Table 3-2](#)). These examinations should be completed within 4 weeks of the relevant study visit. An ophthalmologic examination is also required at the ETT Visit for subjects whose cumulative VX-445/TEZ/IVA exposure (in the parent study and current study) is at least 12 weeks since the last study ophthalmologic examination.

Any clinically significant abnormal findings will be reported as AEs.

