9.1.2 Safety Follow-up

In Parts A and B, the Safety Follow-up Visit is scheduled to occur 28 (\pm 7) days after the last dose of study drug. The Safety Follow-up Visit assessments are listed in [Table 3-1](#) and [Table 3-2](#).

The Safety Follow-up Visit is required for all subjects. However, subjects will complete the respective Part A or Part B Week 96 Visit and will not have a Safety Follow-up Visit if the subject transitions within 28 days of the last dose of study drug to one of the following:

- A commercially available Vertex CFTR modulator regimen,
- Managed-access-program-supplied Vertex CFTR modulator regimen,
- Or, to another Part of the current study or another qualified Vertex study.

If the transition occurs before the Week 96 Visit, then subjects will complete the Early Termination of Treatment (ETT) Visit. In these cases, the Week 96 Visit or the ETT Visit, whichever is applicable, will replace the Safety Follow-up Visit.

For subjects who complete an ETT Visit 3 weeks or later following the last dose of study drug, the ETT Visit will replace the Safety Follow-up Visit (Section [9.1.3](#)).

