9.1.5 Completion of Study Participation

Completion of study participation for each individual subject is defined as: the Safety Follow-up Visit; or, in situations in which the ETT Visit or the Part A or B Week 96 Visit replaces the Safety Follow-up Visit (Section [9.1.2](#)), the ETT Visit or Part A or B Week 96 Visit.

If subjects withdraw consent or assent, completion of study participation is defined as date of withdrawal of consent or assent, whichever is earlier (Section [9.9](#)).

If subjects are lost to follow-up (Section 9.1.4), the date of completion of study participation will be defined as the date of last contact.

The end of study is defined in Section 13.2.8.

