12.3.4.1 Adverse Events

For analysis purposes, AEs will be classified as pretreatment AEs, TEAEs, or post-treatment AEs, defined as follows:

- **Pretreatment AE:** any AE that occurred before the first dose of study drug in the TE Period in each Part
- **TEAE:** any AE that worsened (either in severity or seriousness) or newly developed at or after the first dose date of study drug in the TE Period in each Part
- **Post-treatment AE:** any AE that worsened (either in severity or seriousness) or newly developed after the TE Period in each Part

For AEs with missing or partial start dates, if there is no clear evidence that the AEs started before or after study drug treatment, then the AEs will be classified as TEAEs.

AE summary tables will be presented for TEAEs only and will include the following:

- All TEAEs
- TEAEs by strongest relationship
- TEAEs by maximum severity
- TEAEs leading to treatment discontinuation
- TEAEs leading to treatment interruption
- Serious TEAEs
- TEAEs leading to death
- Grade 3 and Grade 4 TEAEs
- Frequently reported TEAEs

Summaries will be presented by MedDRA SOC and PT using frequency counts and percentages (i.e., number and percentage of subjects with an event). When summarizing the number and percentage of subjects with an event, subjects with multiple occurrences of the same AE or a continuing AE will be counted once, only the maximum severity level will be presented in the severity summaries, and the strongest relationship level in the relationship summaries. An AE

overview table will be provided. In addition, a listing containing individual subject level AE data for all deaths and other serious and significant AEs will be provided separately. All AEs, including pre- and post-treatment AEs, will be presented in individual subject data listings.

Exposure-adjusted event rates may also be provided.

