13.1.1.3 Documentation of Adverse Events

All AEs will be collected from the time the ICF is signed until the completion of study participation (Section 9.1.5).

All subjects' parents or legal guardians will be queried, using nonleading questions, about the occurrence of AEs at each study visit. When possible, a constellation of signs and/or symptoms will be identified as 1 overall event or diagnosis. All AEs for enrolled subjects will be recorded in the CRF and source document. The following data will be documented for each AE:

- Description of the event
- Classification of "serious" or "nonserious"
- Date of first occurrence and date of resolution (if applicable)
- Severity
- Causal relationship to study drug(s)
- Action taken
- Outcome
- Concomitant medication or other treatment given

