9.3 Analysis Period for Final Analysis

OLE Efficacy Period: Time from the first dose of study drug in the OLE study to the last efficacy assessment, which may be collected up to OLE Part B Week 96 Visit or the earlier of Day 1345 and the end of study participation if subject does not have the OLE Part B Week 96. This analysis period will be used with the OLE-FAS to analyze efficacy data in the Week 144 IA and the final analysis.

OLE Safety Period: Time from the first dose of study drug in the OLE study to 28 days after the last dose of the study drug in the OLE study or to the completion date of study participation (as defined in Section 9.1.5 of the CSP), whichever occurs first.

The completion date of study participation will be obtained from the end of study page of the eCRF.

The **OLE Treatment-emergent (TE) Period** is same as the OLE Safety Period.

The OLE Cumulative TC Efficacy Period: For subjects who enrolled in the OLE study, the time from the first dose of study drug in the parent study (445-106 Part B) until the last efficacy assessment in the OLE study, which may be collected up to the Part B Week 96 Visit or the earlier of Day 1345 and the end of study participation if subject does not have the Part B Week 96 Visit. For subjects who did not enroll in the OLE study and were enrolled and received study drug in the parent study, definition of this analysis period is the same as the parent study efficacy period.

The Cumulative TC Efficacy periods will be used with the Cumulative TC sets for analysis of PEx data.

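### When a subject leaves at Week 96 for another Vertex regimen, AE collection and the TE Period close that day, yet the required eye examination may come up to 28 days later

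*Protocol*

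**What the plan says.** - **Examination.** Protocol Tables 3-1 and 3-2 schedule eye examinations at Weeks 48 and 96 in Part A, and at Week 96 only in Part B. Section 11.5.5 adds the timing rule, "These examinations should be completed within 4 weeks of the relevant study visit", and the reporting rule, "Any clinically significant abnormal findings will be reported as AEs". The reporting rule has no closing date.
- **Leaving the study.** Protocol 9.1.2 waives Safety Follow-up for a subject who switches to a commercial or managed-access Vertex modulator, another Part, or another qualified Vertex study. Its condition reads: "will not have a Safety Follow-up Visit if the subject transitions within 28 days of the last dose of study drug". Section 9.1.5 normally ends participation at Safety Follow-up, with one exception that matters here: "in situations in which the ETT Visit or the Part A or B Week 96 Visit replaces the Safety Follow-up Visit". Completion is then the replacing visit itself.
- **AE collection.** Protocol 13.1.1.3: "All AEs will be collected from the time the ICF is signed until the completion of study participation".
- **TE Period.** SAP 9.3 runs the OLE Safety Period, which is also the TE Period, from first dose "to 28 days after the last dose of the study drug in the OLE study or to the completion date of study participation", taking the earlier date. SAP 9.2 (Part A) and Protocol 12.3.1 (each Part) use the same rule.
- **Reporting.** Protocol 12.3.4.1: "AE summary tables will be presented for TEAEs only". SAP 10.4.1.1 and 10.4.2.1 class an AE that begins or worsens after the period as post-treatment and place it in a listing. SAP 10.4.1.6 and 10.4.2.6 give eye-examination results in listings only.

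**The concern.** Each rule is reasonable alone; together they leave a gap. The examination is required and may take place after the visit, but for subjects who leave at Week 96 the visit date closes both AE collection and the TE Period. A site that finds a lens change ten days after the visit has two instructions: 11.5.5 tells it to report an AE, while 13.1.1.3 says collection has ended. If the AE is entered with the examination date as onset, the SAP classes it as post-treatment and it leaves the tables.

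Ophthalmologic examination is named in the primary endpoint (Protocol 7.1, SAP 6.1), and Protocol 9.3.3 describes it as recommended monitoring for children on ivacaftor-containing regimens. The SAP plans no table of eye results, and its lists of safety endpoints in 10.4.1 and 10.4.2 omit ophthalmology. The TEAE tables are therefore the only planned tabulation in which a lens finding could appear. In Part B the affected examination is the only scheduled one in 96 weeks, and Week 96 is when completers would move to another supply of drug.

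**Working it through.** The documents derive no figure on this point, and no power or sample-size formula applies. The check is a timeline.

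Inputs:
- Day 0 is the Week 96 Visit.
- Last dose is the evening before, day -1 (Tables 3-1 and 3-2, study drug dosing row).
- The latest permitted examination is day +28 (11.5.5).
- Safety Follow-up, where it applies, is 28 ± 7 days after last dose (9.1.2).
- End of AE collection = completion of participation.
- End of TE Period = min(last dose + 28 days, completion).

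For a subject who leaves at Week 96, completion is day 0:
- AE collection ends on day 0.
- The TE Period ends on min(-1 + 28, 0) = min(27, 0) = day 0.
- Post-visit examination days are +1 to +28, and 28 of 28 lie outside both.

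For comparison:

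| Subject | AE collection ends | TE Period ends | Post-visit days outside TE | Outside AE collection |
|---|---|---|---|---|
| Leaves at Week 96 | day 0 | day 0 | 28 of 28 | 28 of 28 |
| Safety Follow-up at last dose + 21 | day 20 | day 20 | 8 of 28 | 8 of 28 |
| Safety Follow-up at last dose + 28 | day 27 | day 27 | 1 of 28 | 1 of 28 |
| Safety Follow-up at last dose + 35 | day 34 | day 27 | 1 of 28 | 0 of 28 |

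The gap is thus almost entirely a matter of the waived Safety Follow-up Visit.

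The share of final examinations that falls in the gap depends on when they are done. It is 0% if all are on or before the visit and 100% if all are after it. If they were spread evenly over the 28 days before, the visit day and the 28 days after (an assumption), it would be 28/57 = 49%. These are shares of examinations, not of subjects with a finding.

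For scale, 64 subjects enrolled (SAP 7.2), so one event is 1/64 = 1.6% of everyone enrolled. The number who left at Week 96 for another regimen is not given.

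**The case against.** Several objections limit the point, and they stand.

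- **Early termination.** A reader might extend the argument to the ETT Visit. The text does not support that. The 4-week rule follows a sentence about Treatment Period visits, whereas the ETT requirement is separate ("An ophthalmologic examination is also required at the ETT Visit for subjects whose cumulative VX-445/TEZ/IVA exposure" passes a 12-week threshold) and states no window.
- **Reporting is not clearly barred.** Section 11.5.5 can be read as a specific rule that outlasts the general cut-off, since the neighbouring ECG section (11.5.4) does limit AE recording to completion of participation and 11.5.5 does not. The SAP also takes the completion date from the eCRF end-of-study page, so a site might enter a later date. The definition the SAP cites is still the visit, so this shows ambiguity and does not settle it.
- **Examination date is not automatically onset.** TEAE status follows when the event developed or worsened. An earlier recorded onset makes it a TEAE. Under SAP Appendix D, a missing day becomes the first of the month, or the first-dose day if the month is the same, which can place onset before Week 96. Without clear evidence otherwise, an AE with a missing or partial start date defaults to a TEAE.
- **Findings are not lost.** They stay in the ophthalmology listing and, if reported, in the AE listing. Related SAEs after Safety Follow-up remain reportable (13.1.2.2). With 64 subjects, a reader of the listings could find them.
- **Rollovers.** SAP 3.1 pools safety across Parts, so a subject who continues into Part B is covered in the pooled OLE analysis, though not in the Part A TE Period.
- **The present rule has a purpose.** It keeps events that begin on another regimen out of this study's TEAEs.

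These narrow the scope. None extends AE collection or the TE Period to a delayed Week 96 examination.

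**Conclusion.** The gap is real but narrow. It concerns subjects who leave at Week 96 of Part B, or of Part A without entering Part B, for a commercial, managed-access or other-study Vertex regimen within 28 days of last dose, and whose eye examination follows the visit. For them 11.5.5 conflicts with 9.1.5 and 13.1.1.3 on whether a clinically significant finding is collected. If onset is dated at the examination, the finding is post-treatment and appears in no table.

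A reader might infer that lens events vanish, or that about half are missed. The documents support neither: findings remain in listings, and the 49% rests on an assumed even spread inside a 0% to 100% range. Examinations on or before the visit and findings with earlier or imputed onset are unaffected.

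Where the gap operates on a change that arose on treatment, it lowers the TEAE count. An event that truly began after the switch is correctly excluded now.

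**What to change.** - **Protocol.** Reconcile 11.5.5 with 9.1.5 and 13.1.1.3: keep AE collection for eye findings open until the required Week 96 examination is done, within its existing 4-week limit.
- **SAP 9.2 and 9.3.** State that a clinically significant finding at that examination counts as treatment-emergent unless its onset is documented as after the switch to the other regimen. Flag findings detected after the visit in the listing.

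The cost is wording in two documents and an AE page left open for up to four more weeks for one item. No visit or examination is added. SAP section 4 provides for revision by amendment before the Week 144 data cutoff.

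There is a small downside. A finding up to about four weeks after the last study dose may be attributed to this study, and for a subject entering another Vertex study it could be counted in both. The onset exception and the listing flag limit this.
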